### **7.2.4 Laboratory assessments**

#### **7.2.4.1 Type of laboratory**

A central laboratory [see central laboratory manual for contact details, page [2](#)] will be used for all protocol-mandated laboratory tests, including re-tests due to laboratory abnormalities and laboratory tests performed at unscheduled visits.

If the results from the central laboratory are not available in time for enrollment of the participant, an additional blood sample may be drawn to verify eligibility based on a local laboratory test. The local laboratory results (with the corresponding normal ranges) must be recorded in the eCRF.

Other exceptional circumstances that require the recording of local laboratory results of the parameters are described in Section 7.2.4.2 (with corresponding normal ranges), including hospitalization of the participant due to a medical emergency and missing central laboratory results from a scheduled or unscheduled visit.

If one or more central laboratory samples are lost or cannot be analyzed for whatever reason, the investigator will collect an additional sample as soon as possible to repeat the analysis, unless a local laboratory sample was collected within the same time-window and these test results are available.

After Week 16, under specific circumstances (eg, if the participant lives far from the site and cannot return to the site), laboratory samples may be collected at a laboratory close to where the participant lives (satellite laboratory) and sent to the central laboratory for analysis. In such cases, the satellite laboratory must be provided with the central laboratory sampling kits. Shipment of the samples will be organized by the satellite laboratory. If this process is implemented, the satellite laboratory must be identified prior to enrollment of the participant in the study. The supervision of the satellite laboratory remains the responsibility of the PI.

Central laboratory reports will be sent to the investigator. In the case of specific (pre-defined) laboratory abnormalities, the central laboratory will alert the Sponsor personnel and the concerned site personnel. Alert flags that will trigger such notifications are displayed in the central laboratory manual, provided separately.

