#### **10.3.5.3 Laboratory variables**

All laboratory data transferred are taken into account regardless of whether they correspond to scheduled (per protocol) or unscheduled assessments. All recorded assessments will be assigned to the most appropriate visit time points according to the best fitting time-window for that assessment using the usual location and scale summary statistics.

For each laboratory variable, the number and percentage of participants with at least one treatment-emergent marked abnormality will be summarized up to EOT + 3 days.

The change in selected laboratory values and the change in TSH will also be summarized over time up to EOT + 3 days, using the same descriptive statistics for continuous variables.

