2. ANALYSIS DETAILS

2.1. Analysis Sets

- **Screened Analysis Set:** Screened analysis set includes all participants who are screened and have a participant identification number.
- **Full Analysis Set:** Full analysis set includes all enrolled participants who were eligible to receive the study drug.
- **Safety Analysis Set:** Safety analysis set includes all participants included in Full Analysis Set who receive at least one dose of the study drug. Since all enrolled participants received at least one dose of study drug, the Full Analysis Set and Safety Analysis Set are the same in this study. For simplicity, the Safety Analysis Set will be used for all safety and efficacy analyses.
- **Pharmacokinetic Analysis Set (PKS):** PK analysis set comprises all participants included in the Safety Analysis Set who complied with the protocol sufficiently and did not deviate from the protocol in a way that might affect the PK outcome of the study. Criteria for sufficient compliance include exposure to treatment, availability of PK measurements, and absence of major protocol deviations that have an impact on the PK. Further details are provided in the PK and modeling analysis plan.

For all analyses, except the time to disease progression event, only the scheduled visits data will be used in summary outputs; both the scheduled and unscheduled visits data will be included in the listings.

The analysis set usage is summarized as following:

Table 2: Study Analysis Set Usage

	Screened Analysis Set	Full Analysis Set	Safety Analysis Set	PK Analysis Set	PK
Participant disposition	X	X	X		
Participant information (medical history, concomitant medication, contraceptives)			X		
Participant information (demographics, baseline characteristics, baseline disease characteristics)			X		
Treatment exposure, treatment discontinuation, drug accountability and compliance, protocol deviation			X		
Safety analyses			X		
Other endpoints analyses			X		
PK analyses				X	X
Efficacy exploratory analyses			X		
Sensitivity Analysis, for Efficacy exploratory analyses			X		
All listings for disposition/Recruitment	X	X	X		
All listings for Participant information	X	X	X		
All other Listings			X		

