4.2. Clinical Laboratory Tests

The following laboratory parameters are evaluated:

- Hematology:
 - Hemoglobin (g/L)
 - Hematocrit (L/L)
 - Erythrocyte count ($10^9/L$)
 - Leukocyte count with differential counts ($10^9/L$)
 - Platelet count ($10^9/L$)
- Clinical chemistry:
 - Alanine aminotransferase (U/L)
 - Aspartate aminotransferase (U/L)
 - Alkaline phosphatase (U/L)
 - Total and direct bilirubin ($\mu\text{mol/L}$)
 - Creatinine ($\mu\text{mol/L}$)
 - Creatinine clearance (mL/min)
 - Serum urea nitrogen (mmol/L)
 - Uric acid ($\mu\text{mol/L}$)
 - Glucose (mmol/L)
 - Cholesterol, triglycerides (mmol/L)
 - Sodium, potassium, chloride, calcium (mmol/L)
 - Albumin (g/L)
 - NT-pro BNP (pmol/L)
 - TSH (mU/L)
 - Free T3 and free T4 (pmol/L)
 - Thyroid antibodies (U/mL)

In addition, local laboratory parameters might be available under certain circumstances and recorded in the CRF.

All recorded assessments, whether from central or local laboratory (including unscheduled) will be assigned to the most appropriate visit time points according to the best fitting time-window for that assessment

If data from a local laboratory and from the central laboratory are available for the same date, the central laboratory value will be used; if more than one valid assessment are available on the same timepoint window in the same lab, the mean value will be considered.

A laboratory test abnormality is defined as any value outside the normal range as provided by the laboratory. The direction of the abnormality (below or above the normal range) is indicated using 'H' and 'L', if applicable.

A marked (alert) laboratory test abnormality is defined as any value that fulfills the applicable condition listed in the table below for LL / HH (or LLL / HHH, respectively):

Safety parameter	Marked Abnormally Low Values		Marked Abnormally High Values	
	LL	LLL	HH	HHH
Hematology				
Hemoglobin (g/L)	< 100	< 80	Increase (> 20 g/L) above ULN or above baseline if baseline is above ULN	Increase (> 40 g/L) above ULN or above baseline if baseline is above ULN
Hematocrit (L/L)	< 0.28 F < 0.32 M	< 0.20	> 0.55 F > 0.60 M	> 0.65
Erythrocyte count (10 ⁹ /L)	NA	NA	NA	NA
Leukocyte count with differential counts (10 ⁹ /L)	< 3.0	< 2.0	> 20.0	> 100.0
Platelet count (10 ⁹ /L)	< 75	< 50	> 600	> 999
Clinical chemistry				
AST (U/L)	NA	NA	> 3 ' ULN	> 5 ' ULN
ALT (U/L)	NA	NA	> 3 ' ULN	> 5 ' ULN
Alkaline phosphatase (U/L)	NA	NA	> 2.5 ' ULN	> 5 ' ULN
Total bilirubin (µmol/L)	NA	NA	> 2 ' ULN	> 5 ' ULN

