Direct bilirubin (µmol/L)	NA	NA	> 2 ' ULN	> 5 ' ULN
Creatinine (µmol/L)	NA	NA	> 1.5 ' ULN or > 1.5 ' baseline if baseline is above ULN	> 3 ' ULN or > 3 ' baseline if baseline is above ULN
Serum urea nitrogen	NA	NA	> 2.5 x ULN	> 5 x ULN
Glucose (mmol/L)	< 3.0	< 2.2	> 8.9	> 13.9
Sodium (mmol/L)	NA	< 130	> 150	> 155
Potassium (mmol/L)	< 3.2	< 3.0	NA	> 6.0
Calcium (mmol/L)	< 2.0	< 1.75	> 2.9	> 3.1

ALT = alanine aminotransferase; AST = aspartate aminotransferase; F = female; M = male; ULN = upper limit of normal range.

Treatment-emergent marked laboratory abnormalities are defined as all marked laboratory abnormalities with onset after the study treatment start and up to EOT+3 days, that were not present at baseline or worsened during the course of the study. They will be analyzed on the Safety Analysis Set overall, by age cohort and body weight group.

For each category (i.e., LL, LLL, HH, HHH), treatment-emergent marked laboratory abnormalities are summarized for each laboratory variable overall, by age cohort and body weight group, displaying counts and percentages of participants with at least one marked treatment-emergent abnormality. Percentages are calculated by dividing the number of participants with at least one marked abnormality for the parameter under consideration by the number of participants with any post-baseline measurement.

The number of participants with laboratory abnormalities/marked abnormalities (any value outside the normal ranges for the laboratory) will be also tabulated as shift tables against baseline.

Absolute values and changes from baseline will be determined for each parameter and participant at the different timepoints of assessment and summarized overall, by age cohort and body weight group for the Safety Analysis Set. For graphs or tables with mean values, to account for changing reference ranges across age and gender, certain central and local laboratory values (Y_{ori}) and their reference ranges (LLN_{ori} , ULN_{ori}) will be normalized as Y_{norm} using a standard range (LLN , ULN) as follows:

$$Y_{norm} = LLN + \frac{(Y_{ori} - LLN_{ori})}{(ULN_{ori} - LLN_{ori})} \times (ULN - LLN)$$

If the value is negative after normalization, zero will be assigned.

The laboratory tests that require normalization and their standard ranges to be used are:

- TSH: 0.34 - 5.60 (mIU/L)
- Free T3: 4.5 - 7.8 (pmol/L)
- Free T4: 10 - 24 (pmol/L)
- Hemoglobin: 116 - 164 (g/L)
- Hematocrit: 0.34 - 0.48 (L/L)

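### The SAP does not exempt marked-abnormality flags from its window-mean rule for laboratory values, so a retest could downgrade or remove a flag

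*SAP*

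**What the plan says.** SAP 4.2 sets out the handling of laboratory data in this order.

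- **Windowing.** Results, "whether from central or local laboratory (including unscheduled) will be assigned to the most appropriate visit time points".
- **Two laboratories.** "If data from a local laboratory and from the central laboratory are available for the same date, the central laboratory value will be used".
- **Several values from one laboratory.** "if more than one valid assessment are available on the same timepoint window in the same lab, the mean value will be considered".
- **Marked abnormality.** "A marked (alert) laboratory test abnormality is defined as any value that fulfills the applicable condition listed in the table below", with grades LL, LLL, HH and HHH.
- **Summary.** Tables "displaying counts and percentages of participants with at least one marked treatment-emergent abnormality", overall, by age cohort and by body weight group. Shift tables against baseline and a separate listing of marked abnormalities are also planned.

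Three other places bear on this. Protocol 7.2.4.1 uses the central laboratory for all mandated tests, "including re-tests due to laboratory abnormalities and laboratory tests performed at unscheduled visits". Protocol 10.3.5.3 says: "All laboratory data transferred are taken into account regardless of whether they correspond to scheduled (per protocol) or unscheduled assessments"; it mentions no averaging. SAP 2.1 says that, for every analysis except time to disease progression, "only the scheduled visits data will be used in summary outputs".

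**The concern.** The mean rule carries no limit and stands directly before the flag definitions. Elsewhere in SAP 4.2 the authors do limit a rule when they intend to: the normalisation to a standard range is confined to displays of means. A programmer working through the section in order could therefore compute the window mean first and flag that.

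Retests normally satisfy the same-laboratory condition, because the protocol sends them to the central laboratory. The SAP gives no window widths, but every result must be placed in a window, and after Week 16 the site visits in Protocol Table 5 are 3 and later 6 months apart. A recovered value taken well after an abnormal one could fall in the same window.

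Treatment-emergent marked laboratory abnormalities are a named safety endpoint (Protocol 6.2 and 10.2.4). Haemoglobin is a parameter of interest: Protocol 1.2.3.4.2 reports small reductions in the adult trial, and anaemia is an adverse event of special interest in SAP Appendix 2.

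**Working it through.** The documents give no figure for this rule, so there is none to reproduce. The check compares two readings of SAP 4.2: flags from individual values, and flags from the window mean.

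**Direction.** Take a fixed high cut-off T. If every value in the window is at or below T, so is their mean. A mean above T therefore requires at least one value above T. The same holds in reverse for a low cut-off. Averaging cannot create a marked flag that no single value earned; it can only keep, downgrade or remove one. This is true whatever prompted the second sample.

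**When a flag is lost.** With a first value x beyond T and one retest y, the mean is (x + y)/2. The flag is lost when y ≤ 2T − x on the high side, or y ≥ 2T − x on the low side.

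- ALT, T = 3 × ULN, x = 3.4: lost if y ≤ 2(3) − 3.4 = 2.6.
- Potassium, T = 6.0 mmol/L, x = 6.2: lost if y ≤ 2(6.0) − 6.2 = 5.8.
- Haemoglobin, x = 78 g/L: LLL lost if y ≥ 2(80) − 78 = 82; LL also lost if y ≥ 2(100) − 78 = 122.

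**Worked pairs.** Cut-offs are from SAP 4.2. The value pairs are assumed.

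| Test | First | Retest | Mean | Individual values | Window mean |
|---|---|---|---|---|---|
| ALT (× ULN) | 3.4 | 2.2 | 2.8 | HH | none |
| ALT (× ULN) | 6 | 2 | 4.0 | HHH | HH |
| ALT (× ULN) | 8 | 2.5 | 5.25 | HHH | HHH |
| Haemoglobin (g/L) | 78 | 104 | 91 | LLL | LL |
| Haemoglobin (g/L) | 95 | 110 | 102.5 | LL | none |
| Platelets (10⁹/L) | 60 | 120 | 90 | LL | none |
| Potassium (mmol/L) | 6.2 | 4.8 | 5.5 | HHH | none |
| Sodium (mmol/L) | 128 | 136 | 132 | LLL | none |

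Five pairs lose the flag, two drop a grade and one is unchanged. High potassium and low sodium have no middle grade, so nothing catches the case once the extreme flag is gone. The pairs show the mechanism and say nothing about its frequency.

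**Unit of loss.** One participant is 1/60 = 1.7 percentage points of the planned total and 1/20 = 5 points of a planned age cohort. The SAP's denominator is participants with any post-baseline measurement, so the actual steps would be at least this large if some have none.

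**If SAP 2.1 governs instead.** An unscheduled retest then stays out of the summary and cannot dilute a scheduled value. But a marked value found only at an unscheduled visit is not counted either, which contradicts SAP 4.2 and Protocol 10.3.5.3. Counts can fall short under this reading too, by a different route.

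**The case against.** The strongest reply is that the SAP already flags from individual results. A marked abnormality is any value meeting the condition, participants are counted if they have at least one, and a single value per window is needed only for by-timepoint summaries. This is a fair reading and may be what was meant. It does not close the point: the text does not say whether a value is the raw result or the mean just prescribed, and two competent programmers could produce different endpoint counts.

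A reader might infer several stronger claims that the documents do not support.

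- *That the SAP averages before it flags.* The order of the two steps is not stated.
- *That all laboratory values are averaged.* The rule covers one laboratory within one window. A same-date local value is replaced by the central one, not averaged with it.
- *That the rule bites only after an abnormal result, or that second values are mostly retests.* Protocol 7.1.2 allows unscheduled visits for any reason, and Protocol 7.2.4.1 provides for redrawing lost samples. No source gives the mix.
- *That abnormal results vanish.* All individual results are listed, the central laboratory alerts site and sponsor to predefined abnormalities, and clinically relevant ones must be reported as adverse events. What is at risk is the flag in the summary and shift tables, and in the separate listing of marked abnormalities.

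The alerts and adverse event reports limit the harm to oversight of individual children. They do not replace the table, which applies fixed thresholds where adverse event reporting depends on the investigator's judgement.

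**Conclusion.** The point holds as an unlimited rule with a consequence, not as a demonstrated under-count. SAP 4.2 leaves the marked-abnormality flags exposed to the window mean. If they are derived that way, the error for a fixed cut-off goes in one direction only, towards fewer or milder abnormalities on a named safety endpoint. If SAP 2.1 is applied instead, marked values seen only at unscheduled visits drop out. Only flagging from individual values, unscheduled ones included, avoids both.

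The frequency in this trial cannot be estimated from the documents. The conclusion on averaging assumes that a retest comes from the same laboratory and falls in the same window, and that flags are taken from the mean. It merits correction because the endpoint is prespecified, the groups are small and the remedy is cheap.

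**What to change.** Amend the SAP as follows.

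1. In 4.2, limit the mean rule to by-visit summaries of continuous values and changes from baseline.
2. In 4.2, derive the treatment-emergent marked-abnormality counts and their listing from every individual post-baseline value, scheduled or unscheduled, up to EOT + 3 days, taking the worst value per participant and direction (lowest for LL/LLL, highest for HH/HHH).
3. Keep the by-visit shift tables described in SAP 7, using the worst individual value within each window. They need not become whole-period worst-value tables.
4. In 2.1, exempt the laboratory abnormality tables from the scheduled-visits-only rule, so that 2.1 agrees with 4.2 and with Protocol 10.3.5.3.

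The preference for central over same-date local results is a separate choice; the new text should say whether it also applies to flags. The cost is a few sentences and a programming flag. No new data are needed.

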	
≥ 2 years of age. A final PK analysis will be prepared based on the overall PK and safety data up to Week 16 evaluation.
 
The selection of the dosing regimen for the Phase 3 study will be based on the safety, tolerability, and PK results evaluated in the interim or final PK analysis (as applicable).
 
Participants who discontinue treatment any time before the profile PK sampling day may be replaced within their age cohort.

PERIODS	
The study consists of the following consecutive periods:
 
Screening period: Lasts up to 6 weeks; starts with the signature of the informed consent form (ICF) and ends with the administration of the first study treatment dose.
 
Treatment period: Starts from the first dose of study treatment at Baseline/Enrollment visit and ends on the day of the last dose of selexipag (End-of-Treatment [EOT] visit). This includes:
 
 
• Up-titration period: From the first dose of study treatment until the participant reaches their individual maximum tolerated dose (iMTD). This period is estimated to last up to 12 weeks.
 
• Maintenance period: 
 
After Week 12: the participants will continue study treatment at the same dose up to Week 16.
 
After Week 16: study treatment will continue as long as it remains beneficial for the participant [see Section 3.1.2 for details].
 
 
 
 
EOT visit: this visit should be conducted within 1 week of the last dose of study treatment. The participant will then enter the Safety follow-up period.
 
Safety follow-up period: Starts on the day after the last dose of study treatment and ends 30 days thereafter. This period ends with a phone call that indicates the End-of-Study (EOS).

PLANNED DURATION
	
Approximately 7 years from first participant, first visit to last participant, last visit.

SITE(S) / COUNTRY(IES)
	
Approximately 30 sites in 20 countries (planned).

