## 7 VISIT SCHEDULE AND STUDY ASSESSMENTS

### 7.1 Study visits

The study visits are listed in [Table 4](#) and [Table 5](#). For all visits, the participants must be seen on the designated day with an allowed visit window indicated in the tables. An EOT visit must be performed within 7 days of intake of the last dose of study treatment. A safety follow-up call should follow 30 days after this visit, and will be considered the EOS for an individual participant.

All assessments pertaining to a visit should be performed on the same day. If this is not possible, the visit may extend over more than 1 day within the allowed time window.

If study treatment is prematurely discontinued, the EOT visit must take place as soon as possible and no later than 7 days after the last dose of study treatment. A safety follow-up call should follow 30 days after this visit.

Participants who prematurely discontinue study treatment / study participation for any reason before contributing to PK sampling, or for whom PK samples are missing / have been mishandled, may be replaced.

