**Table 5 Visit and assessment schedule after Week 16**

Period	Site visits for participants during the first 12 months following Week 16 (M4)	Site visits for participants after 12 months	Phone calls for participants after 12 months	Unscheduled visit	End-of-Treatment	Safety follow-up Tel.
Name	Visit 9, 10, 11, 12	Visit 13, 14, 15 ...	Tel.	Unscheduled visit	EOT	EOS
Time e	Site visits every 3 months (M7, M10, M13, M16) ± 15 days	Site visits every 6 months (M22, M28, M34...) ± 15 days	Phone call: every 6 months (M19, M25, M31, M37...) alternating with visits ± 15 days	If medically indicated or recommended for assessing PAH progression	Last dose of study drug + up to 7 days	Phone call: 30 days after last dose of study drug + up to 7 days
Previous/Concomitant medications for PAH	X	X		X	X	
Mod. NYHA/WHO FC	X	X		X	X	
Panama FC	X	X		X	X	
PAH signs/symptoms	X	X		X	X	
PAH-related non-pharmacological interventions	If applicable					
Physical examination	X c	X c		X	X c	
Growth: Weight and height	X	X		X	X	
Vital signs (blood pressure, heart rate,)	X	X		X	X	
Echo	X d			X	X	
6MWD test	X b	X		X	X	
Tanner stage	X	X				
Childbearing potential	X	X	X	X	X	
Pregnancy test (if appl.)	X	X	X a	X	X	X
Laboratory test (Hematology/Chemistry)	X	X		X	X	
TSH	X	X		X	X	
Thyroid antibodies	X when medically indicated					
T3 and T4	X when TSH is abnormal or when medically indicated					
Plasma NT pro-BNP	X	X		X	X	
ECG	X	X			X	
Study drug dispensing	X	X		X		
Drug accountability	X	X		X	X	

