#### **10.3.5.6 Height and Weight**

Absolute values and changes from baseline will be summarized over time up to EOT + 3 days, using descriptive statistics for continuous variables.

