4.5. Electrocardiograms

ECG will be evaluated by a central ECG service. All ECG data from scheduled and unscheduled visits will be listed.

The quantitative ECG variables up to EOT + 3 days that will be summarized are heart rate (bpm), RR interval (msec), PR interval (msec), QRS interval (msec), QT interval (msec), QTcB (msec) and QTcF (msec), the corrected QT (QTc) using Bazett's and Fridericia's methods, respectively. Values at all scheduled visits and changes from baseline (last value assessed before first study dose intake) over time will be summarized by parameter, time point, age cohort and body weight, and will be presented in figures as well.

In addition, QTcB and QTcF will also be summarized by age cohort and the following categories:

- Value ≤ 450 (normal)
- Value $> 450 - \leq 480$
- Value $> 480 - \leq 500$
- Value > 500
- Increase from baseline ≤ 30
- Increase from baseline $> 30 - \leq 60$
- Increase from baseline > 60
- Value > 480 and increase from baseline $> 30 - \leq 60$
- Value > 480 and increase from baseline > 60

For Week 1 and Week 12, where two additional ECG assessments are done at 2H and 4H post-dose, only pre-dose data will be included in the overall analysis. In addition, separate analyses will be done with only Week 1 and Week 12 ECGs data, where values and change from pre-dose to post-dose at each visit will be summarized by parameter, abnormality category for QTcB/F, time

point, and age cohort. Furthermore, summary of QTcF/B abnormalities by category over time and shift tables will be provided for both the overall analysis and Week 1 & 12-focused analysis.

The qualitative ECG abnormal findings at study baseline will be summarized by age cohort and are defined as following:

- Atrioventricular Conduction - 1st Degree Av Block
- Chamber Hypertrophy or Enlargement - Left Atrial Abnormality
- Chamber Hypertrophy or Enlargement - Left Ventricular Hypertrophy
- Chamber Hypertrophy or Enlargement - Right Atrial Abnormality
- Chamber Hypertrophy or Enlargement - Right Ventricular Hypertrophy
- Interpretation - Abnormal
- Interpretation - Not Evaluable
- Intraventricular-Intraatrial Conduction - Incomplete Right Bundle Branch Block
- Intraventricular-Intraatrial Conduction - Intraventricular Conduction Delay, Nonspecific
- Intraventricular-Intraatrial Conduction - Left Posterior Fascicular Block
- Intraventricular-Intraatrial Conduction - Right Bundle Branch Block
- ST Segment, T wave, and U wave - QTc Prolongation

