4.6. Vital Signs

The vital signs parameters up to EOT + 3 days that will be analyzed are heart rate and blood pressure (systolic and diastolic). Position and location will only be listed.

Values and change from baseline over time will be summarized by parameter and time point, age cohort and be presented in figures as well.

All individual vital signs data will be listed.

Body Weight and Height

Height (m) (measured at Screening and Week 16) and weight (kg) data will be used in calculating the BMI.

BMI (kg/m²) will be calculated at each of these time-points. Before Week 16, BMI is calculated by using height from screening, and at Week 16 will be calculated by using height collected at

Week 16. After Week 16, BMI will be calculated from the height and weight collected at each visit.

Values and changes from baseline over time for weight, height and BMI will be summarized by age cohort and body weight group.

All individual height, weight and BMI data will be listed, and the growth curves will be presented for height, weight, and BMI as well.

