AE resolution date	The earlier of the Upper limit and the end of study date	No replacement, considered ongoing at end of study
AE onset date	If the end date of the AE is not before the start of study drug, and if the study drug start falls in the range of possible dates, it is the study drug start date. In all the other cases, it is the lower limit	The earlier of the end date of the AE and the start of study drug
Concomitant medication start date	Lower limit	No replacement, the medication is considered to have started before the study
Concomitant medication end date	The earlier of the Upper limit and the end of treatment date	No replacement, considered ongoing at end of treatment
Death date	Last of the Lower limit and recorded study assessment dates	Last of the recorded study assessment dates

Anomalous information for a date will be handled using the following rules prior to using the imputations mentioned above:

If the day part of a date is non-numeric or has an invalid value, then day will be considered as missing. For example, if date = 44Nov2000 then, as it isn’t possible to have a 44th day of the month, the day will be considered missing.

If the month part of a date does not match that of the possible months, then it will be considered missing, and so will the accompanying day. For example, if date = 21ND99 then both day and month will be considered as missing.

If the year part of a date is non-numeric or has an invalid value, then the whole date will be considered as missing.

General Conventions:

- Study treatments start date is the first day of intake of study treatment. It is derived as the first 'Treatment start date' after sorting in chronological order all records. It coincides with Study Day 1.
- Study treatment end date (EOT) is the last day of intake of study treatment. It is derived as the last 'Treatment end date' after sorting in chronological order all records.
- Starting dose is the dose given on study treatment start date.

Study Day refers to the number of days elapsed since the day of study treatment start, plus 1 (i.e., Study Day 1 is the day of study treatment start). For dates prior to treatment start, it is the negative number of days elapsed between the date under consideration and the day of study treatment start. Therefore, the study day is always different from 0

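### Safety values from an on-time EOT visit held 4 to 7 days after the last dose fall outside the SAP's EOT + 3 day summaries, and the marked laboratory abnormality rate then has a wider denominator than numerator

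*SAP*

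**What the plan says.** **What EOT means.** SAP section 7 (General Conventions) states: "Study treatment end date (EOT) is the last day of intake of study treatment". EOT + 3 days in the analysis therefore means last dose plus 3 days.

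**When the EOT visit happens.** Protocol section 7.1 states: "An EOT visit must be performed within 7 days of intake of the last dose of study treatment". Protocol Table 5 gives the same window, "Last dose of study drug + up to 7 days", and schedules hematology, chemistry, TSH, ECG, vital signs, weight and height at that visit.

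**Where the SAP stops counting.**
- Laboratory (SAP 4.2): treatment-emergent marked abnormalities are "all marked laboratory abnormalities with onset after the study treatment start and up to EOT+3 days". The percentage is taken over everyone with a measurement at any time after baseline.
- ECG (SAP 4.5): "The quantitative ECG variables up to EOT + 3 days that will be summarized are heart rate (bpm", followed by the intervals and corrected QT. New qualitative findings carry the same limit.
- Vital signs (SAP 4.6): "The vital signs parameters up to EOT + 3 days that will be analyzed are heart rate and blood pressure".

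**Where the two documents differ.** Protocol 10.3.5.3 also stops the laboratory and TSH change summaries at EOT + 3 days. For height and weight, protocol 10.3.5.6 says: "Absolute values and changes from baseline will be summarized over time up to EOT + 3 days". SAP 4.2 states no such limit for laboratory values, changes or shift tables, and SAP 4.6 states none for weight, height or BMI.

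Neither document says how an EOT visit on days 4 to 7 is to be handled.

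**The concern.** Safety and tolerability are the secondary objective. The EOT visit is the last scheduled safety measurement on every child, and for some it is the only one after baseline. In protocol Table 4 the first scheduled post-baseline laboratory, TSH and vital-sign assessments are at Week 4, so a child who stops before then depends on the EOT visit.

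A site can follow the visit window exactly and still produce values that three sets of summary tables leave out. The disease-progression endpoint, by contrast, runs to EOT + 7 days, which matches the visit window.

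The marked-abnormality table raises a second issue. Limiting the numerator but not the denominator treats a child who had no countable sample as a child observed to be free of abnormality.

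**Working it through.** The plan gives no figure to reproduce. The check is window arithmetic plus a comparison of numerator and denominator.

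**1. Overlap of the windows.** Allowed visit days after the last dose (protocol 7.1, Table 5): 0, 1, 2, 3, 4, 5, 6, 7, which is 8 days. Days beyond EOT + 3, with EOT as last intake (SAP 7): 4, 5, 6, 7, which is 4 days.
- Share of allowed days outside the window: 4/8 = 50%.
- If the visit is never on the last-dose day: 4/7 = 57%.

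These are shares of permitted days, not of visits. Visit timing is not given.

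**2. Children affected, under assumed shares of late visits.** Planned enrolment is about 60 (protocol 3.1).

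| Assumed share of EOT visits on days 4 to 7 | Children of 60 |
|---|---|
| 10% | 0.10 × 60 = 6 |
| 25% | 0.25 × 60 = 15 |
| 50% | 0.50 × 60 = 30 |

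This is over the whole study, once every child has reached an EOT visit.

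**3. The marked-abnormality percentage.** Let n be the children with any post-baseline sample, k those whose only such sample is on days 4 to 7, x those with a marked abnormality by EOT + 3, and a those whose marked abnormality is seen only at a late EOT visit.
- As written: x / n.
- Both parts cut at EOT + 3: x / (n − k).
- Both parts including the EOT visit: (x + a) / n.

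Both consistent versions are at least as large as x / n, so the written rule can only lower the rate. Each child in a adds 1/60 = 1.7 percentage points overall, or 1/20 = 5 points in a cohort of the planned 20, if all enrolled children have a post-baseline sample. The documents give neither k nor a.

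**4. Is EOT + 3 days reasonable in itself?** Protocol 1.2.3.2 gives the active metabolite's half-life as 6.2 to 13.5 hours. Three days is 72 hours.
- 72/13.5 = 5.3 half-lives, leaving about 2.5%.
- 72/6.2 = 11.6 half-lives, leaving about 0.03%.

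The cut-off is coherent for adverse-event onset. It was not matched to the timing of a scheduled visit.

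**The case against.** **The values are not lost.** A reader might infer that late EOT-visit data are discarded. They are not. SAP 4.2, 4.5 and 4.6 list all individual laboratory, ECG, vital-sign and growth data. Clinically relevant laboratory findings must be reported as adverse events (protocol 7.2.4.1), and adverse events are recorded to EOS (protocol 9.1.4). This stands, but a listing does not correct a percentage in a summary table.

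**The limit does not cover every safety output.** A reader might infer that all measured safety variables stop at EOT + 3 days. Under the SAP that holds for marked laboratory abnormalities, ECG, heart rate and blood pressure. For laboratory and TSH change and for growth, the limit appears only in the protocol. The objection stands; what remains there is a difference to reconcile.

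**On-treatment summaries may exclude off-drug values.** This is a fair argument for ECG and vital signs, given the half-life. It supports flagging late values. It does not support having no rule for a scheduled visit, and it does not justify the unmatched denominator.

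**EOT might mean the visit.** The synopsis says the treatment period "ends on the day of the last dose of selexipag (End-of-Treatment [EOT] visit", which could be read as equating the two. The SAP's own convention settles the matter for the analysis.

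**Late visits may be few.** After premature discontinuation, protocol 7.1 asks for the visit as soon as possible within the 7 days. An even spread over the window therefore cannot be assumed, and the 50% is not an estimate of loss.

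**Conclusion.** The mismatch is real and follows from the documents' own definitions. EOT-visit values from days 4 to 7 are listed but excluded from the SAP's summaries of marked laboratory abnormalities, ECG, heart rate and blood pressure. The marked-abnormality rate is also biased downward whenever a child's only post-baseline sample is a late one.

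The size is unknown. Half of the allowed visit days lie outside the window, and 6 to 30 of 60 children would be affected if 10% to 50% of visits were late; those shares are assumptions. The children who distort the laboratory denominator are a subset, chiefly any who stop before Week 4 and attend late.

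Two stronger readings are not supported. One is that the loss falls mostly on children who stopped early. No figure backs this, and every treated child is due an EOT visit in the end. It fits the Week 16 CSR better, since an EOT visit by then implies early stopping. The other is that these children drop out of the laboratory table and leave it weighted towards those who tolerated the drug. The written denominator keeps them in; the fault is that their events cannot be counted.

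The analyses are descriptive and single-arm, so no test is affected. This is a low-cost improvement to the safety tables.

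**What to change.** 1. Keep EOT + 3 days for adverse-event onset.
2. In SAP 4.2, 4.3, 4.5 and 4.6, include the scheduled EOT-visit laboratory, TSH, ECG, vital-sign and growth values whenever the visit falls within its 7-day window, and show them as a separate EOT-visit row.
3. Count EOT-visit laboratory values in the marked-abnormality table, and define numerator and denominator over the same window.
4. Flag every value taken more than 3 days after last intake.
5. Align protocol 10.3.5.3 to 10.3.5.6 with the SAP at the next amendment.

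**Cost.** SAP wording and programming, with no new data collection. The protocol edits need a written amendment (protocol 12.6), so they are best bundled with the next one. The downside is that some included values, mainly ECG and vital signs, are off drug; the flag and the separate row make this visible.
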